6.1.2 Exclusions to Routine Data Collection

6.1.2.1 Adverse Events

The following events will be captured only in the source documents and will not be recorded:

- All Grade 1 events.
- Grade 2 events that are not related to the treatment.

• Grade 1, 2, and 3 Lab values drawn outside of the protocol specified time points that are not assessed as clinically significant by the PI or his designee and are not associated with an adverse event.

• Events related to vascular access devices (occlusion, thrombi, hospitalizations for insertion or removal).

Note: Events that result in a hospitalization for convenience will not be reported.

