3.1.2 Definition of Dose Limiting Toxicity (DLT)

DLT is defined as:

- Any Grade 3 or greater toxicity that cannot be attributed to a cause other than study treatment during the first two cycles of Course 1 of DAC-THU and/or pembrolizumab therapy such as disease progression or intercurrent illness.
- Any toxicity that cannot be attributed to a cause other than study treatment (DAC-THU and/or Pembrolizumab) that results in study treatment discontinuation.

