3.2.2 Pembrolizumab

Pembrolizumab will be administered as a 30 minute IV infusion every three weeks at a fixed dose of 200 mg/infusion. Subjects may be dosed no less than 12 days from the previous dose of drug. There are no pre-medications recommended for pembrolizumab on the first cycle.

Treatment of Pembrolizumab Related Infusion Reactions:

Since pembrolizumab contains only human immunoglobulin protein sequences, it is unlikely to be immunogenic, and induce infusion or hypersensitivity reactions. However, if such a reaction were to occur, it might manifest with fever, chills, rigors, headache, rash, pruritus, arthralgias, hypo- or hypertension, bronchospasm, or other symptoms. All Grade 3 or 4 infusion reactions should be reported within 24 hours to the study sponsor as an SAE if it meets the criteria. Infusion reactions should be graded according to NCI CTCAE (Version 5.0) guidelines.

Treatment recommendations are provided below and may be modified based on local treatment standards and guidelines, as appropriate:

NCI-CTCAE Grade	Treatment Modification for Pembrolizumab
Grade 1 – mild Mild transient reaction; infusion interruption not indicated; intervention not indicated.	Decrease the pembrolizumab infusion rate by 50%; remain at bedside and monitor closely for any worsening. The total infusion time for pembrolizumab should not exceed 120 minutes.
Grade 2 – moderate Therapy or infusion interruption indicated but responds promptly to symptomatic treatment (e.g., antihistamines, NSAIDs, narcotics, IV fluids); prophylactic medications indicated for \leq 24 hours.	Stop pembrolizumab infusion. Resume infusion at 50% of previous rate once infusion-related reaction has resolved or decreased to at least Grade 1 in severity, and monitor closely for any worsening.
Grade 3 or Grade 4 – severe or life-threatening Grade 3: Prolonged (e.g., not rapidly responsive to symptomatic medication and/or brief interruption of infusion); recurrence of symptoms following initial improvement; hospitalization indicated for clinical sequelae. Grade 4: Life-threatening consequences; urgent intervention indicated.	Stop pembrolizumab infusion immediately and disconnect infusion tubing from the subject. Subjects have to be withdrawn immediately from pembrolizumab treatment and must not receive any further pembrolizumab treatment.

Table 8: Treatment Modification for Pembrolizumab

CTCAE Grade	Treatment Modification for Pembrolizumab
-------------	--

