- Once the pembrolizumab infusion rate has been decreased by 50% or interrupted due to an infusion-related reaction, it must remain decreased for all subsequent infusions.

- If the subject has a second infusion-related reaction Grade ≥ 2 on the slower infusion rate, the infusion should be stopped and the subject should be removed from study treatment.

- If hypersensitivity reaction occurs, the subject must be treated according to the best available medical practice.

IV=intravenous, NCI-CTCAE=National Cancer Institute-Common Terminology Criteria for Adverse Event, NSAIDs=nonsteroidal anti-inflammatory drugs.

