Grade of Rash (NCI-CTCAE v5)	Initial Management	Follow-up Management			
Grade 1 to 2 Covering ≤ 30% body surface area	Continue Pembrolizumab Symptomatic therapy (for example, antihistamines, topical steroids)	If persists > 1 to 2 weeks or recurs: Withhold Pembrolizumab therapy Consider skin biopsy Consider 0.5-1.0 mg/kg/day prednisone or equivalent. Once improving, taper steroids over at least 1 month, consider prophylactic antibiotics for opportunistic infections, and resume Pembrolizumab therapy following steroids taper.			

Dermatological irAEs				
Grade of Rash (NCI-CTCAE v5)	Initial Management	Follow-up Management		
		If worsens: Treat as Grade 3 to 4.		
Grade 3 to 4 Grade 3: Covering > 30% body surface area; Grade 4: Life threatening consequences	 Withhold Pembrolizumab for Grade 3. Permanently discontinue for Grade 4 or recurrent Grade 3. Consider skin biopsy Dermatology consult 1.0 to 2.0 mg/kg/day prednisone or equivalent Add prophylactic antibiotics for opportunistic infections 	If improves to Grade ≤ 1: Taper steroids over at least 1 month; resume Pembrolizumab therapy following steroids taper (for initial Grade 3).		

Pulmonary irAEs				
Grade of Pneumonitis (NCI-CTCAE v5)	Initial Management	Follow-up Management		
Grade 1 Radiographic changes only	Consider withholding Pembrolizumab therapy	Re-assess at least every 3 weeks		
	Monitor for symptoms every 2 to 3 days	If worsens:		
	Consider Pulmonary and Infectious Disease consults	Treat as Grade 2 or Grade 3 to 4.		
Grade 2	Withhold Pembrolizumab therapy	Re-assess every 1 to 3 days		
Mild to moderate new symptoms	 Pulmonary and Infectious Disease consults Monitor symptoms daily; consider hospitalization 1.0 to 2.0 mg/kg/day prednisone or equivalent Add prophylactic antibiotics for opportunistic infections 	If improves: When symptoms return to Grade ≤ 1 , taper steroids over at least 1 month, and then resume Pembrolizumab therapy following steroids taper		
	Consider bronchoscopy, lung biopsy	If not improving after 2 weeks or worsening:		

Pulmonary irAEs		
Grade of Pneumonitis (NCI-CTCAE v5)	Initial Management	Follow-up Management
		Treat as Grade 3 to 4.
Grade 3 to 4 Grade 3: Severe new symptoms; New/worsening hypoxia;	Permanently discontinue Pembrolizumab therapy. Hospitalize.	If improves to Grade ≤ 1 : Taper steroids over at least 1 month

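### Section 6.1.2.1 keeps non-serious, treatment-related Grade 1 events out of the recorded data even when they change treatment, and 6.1.2.2 omits the steroids given for adverse events

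*Combined protocol and SAP*

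**What the plan says.** Section 6.1.1 sets a general rule that adverse events are described in source documents and captured. Section 6.1.2, headed as exclusions to that rule, then narrows it. Of the events listed in 6.1.2.1 it says "The following events will be captured only in the source documents and will not be recorded". The first item is all Grade 1 events, with no condition on relatedness, immune causation or effect on treatment. The item on laboratory values is different: it excludes them only if they are not clinically significant and not tied to an adverse event.

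Section 6.1.2.2 keeps all concomitant medications in source documents. It captures only routine baseline drugs and drugs that cause an adverse event, and names drugs given to treat adverse events among those not captured.

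Elsewhere the protocol acts on Grade 1 events:

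- Section 3.3.6.1, rash of Grade 1 to 2: "If persists > 1 to 2 weeks or recurs: Withhold Pembrolizumab therapy". The same cell adds "Consider 0.5-1.0 mg/kg/day prednisone or equivalent".
- Section 3.3.6.1, Grade 1 pneumonitis: "Consider withholding Pembrolizumab therapy".
- Section 3.3.4: Grade 1 to 2 immune-related events may receive moderate-dose steroids, and persistent ones are managed like Grade 3 to 4.
- Section 3.2.2, Table 8, Grade 1 infusion reaction: "Decrease the pembrolizumab infusion rate by 50" percent. The notes say of a reduced rate that "it must remain decreased for all subsequent infusions".
- Section 3.1.2, second DLT criterion: "Any toxicity that cannot be attributed to a cause other than study treatment (DAC-THU and/or Pembrolizumab) that results in study treatment discontinuation". It sets no minimum grade.

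**The concern.** The first exclusion sorts events by grade alone, whereas the treatment rules also use persistence, recurrence and organ system. A mild event can thus be important enough to change treatment and still be left out of the recorded data. The steroid given for it is left out as well.

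Section 1.1.1 makes defining the toxicities of the combination a Phase I primary objective, and Section 10.1 tabulates recorded toxicity by severity and type. Anyone working from those tables would not see a rash that stopped pembrolizumab for weeks if it stayed at Grade 1 and was not serious.

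The steroid gap is wider than Grade 1, because it also covers steroids given for recorded events of Grade 2 and above. Yet Section 3.3.6.1 requires permanent discontinuation of pembrolizumab when prednisone or equivalent at 10 mg/day or more is needed for more than 12 weeks, other than for adrenal replacement.

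**Working it through.** The plan states no figure to reproduce. The check compares the capture rules with the treatment rules and then bounds the numbers.

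**Rule against rule, for a non-serious, treatment-related Grade 1 event**

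| Event | Protocol action | Firm or optional | Event recorded under 6.1.2.1? |
|---|---|---|---|
| Rash, persistent or recurrent | Pembrolizumab hold | Firm | No |
| Same rash | Prednisone | Optional | No; the drug is not captured either |
| Immune-related event, persistent | Managed like Grade 3 to 4 (3.3.4), for which high-dose steroids are listed | Firm in 3.3.4, subject to the organ tables | No; the drug is not captured either |
| Pneumonitis | Pembrolizumab hold | Optional | No |
| Infusion reaction | Rate halved, then kept reduced | Recommended; may be modified locally | No |
| Any toxicity that ends study treatment | Counts as a DLT | Firm, but rare at Grade 1 | No |

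No other section restores these events. Section 6.1.1 is the general rule to which 6.1.2 makes exceptions. Section 8.2 sends serious events of any grade to the clinical database, so the gap concerns non-serious events only. The graded rows of Table 9 continue DAC-THU at full dose at Grade 1, so the holds and the rate cut at issue concern pembrolizumab.

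**Bounding the numbers**

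Inputs: the adverse event table in Section 1.2.10 for the pembrolizumab arm of the first-line Phase III trial (N = 154), and 16 Phase I patients and a ceiling of 85 from Section 10. The table gives any-grade and Grade 3 to 5 counts but does not separate Grade 1 from Grade 2. The lower bound is therefore zero. For an upper figure, assume that pembrolizumab-alone rates apply and that every Grade 1 to 2 case was Grade 1.

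- Pneumonitis: 9 − 4 = 5; 5/154 = 3.2%.
- Infusion reaction: 7 − 0 = 7; 7/154 = 4.5%.

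Expected count = n × p; chance of at least one = 1 − (1 − p)^n.

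| | Pneumonitis | Infusion reaction |
|---|---|---|
| n = 16, expected | 16 × 5/154 = 0.52 | 16 × 7/154 = 0.73 |
| n = 16, at least one | 1 − (149/154)^16 = 41% | 1 − (147/154)^16 = 52% |
| n = 85, expected | 85 × 5/154 = 2.8 | 85 × 7/154 = 3.9 |
| n = 85, binomial 2.5th to 97.5th percentile | 0 to 6 | 1 to 8 |
| n = 85, expected if half were Grade 1 | 1.4 | 1.9 |

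The pneumonitis column overstates treatment changes further, because the Grade 1 hold is optional. The documents give no rate for persistent or recurrent Grade 1 rash, which is the one firm Grade 1 hold in the organ tables cited here.

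**The case against.** The best defence is that this is a deliberate limit on data entry with a small residue. Every event stays in source documents, is reviewed by a research nurse and is followed whatever its severity. All medications are there too. Most Grade 1 triggers are soft: the pneumonitis hold and the prednisone for rash are only to be considered, and the lead-in to Table 8 lets its recommendations be adapted to local standards. A slower infusion also leaves the 200 mg dose unchanged. All of this stands, and it lowers the weight of the point. It does not answer the firm rash hold, the Section 3.3.4 rule for persistent events or the uncaptured steroids.

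Three stronger readings are tempting, and the documents do not support them.

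- A reader might extend the point to the second exclusion, "Grade 2 events that are not related to the treatment". Section 8.1.5 counts an event as related if there is a reasonable possibility of causation, so a confirmed Grade 2 immune-related event is recorded. A Grade 2 event judged unrelated, including one that leads to a hold while an immune cause is investigated and ruled out, is not a toxicity of the combination. Its omission does not distort the toxicity profile.
- A reader might infer that DLTs would be missed or the MTD misjudged. Section 7.4.1 has the team discuss each patient in detail weekly and base escalation on toxicity data, and Appendix 3 requires weekly adverse event assessment during dose finding. Nothing ties escalation to the recorded subset.
- A reader might infer that the data will show holds or rate changes with no cause attached. The documents do not say whether holds and rates are recorded, or whether a reason is entered with them.

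**Conclusion.** The concern holds in a limited form and merits a cheap improvement. Followed exactly, 6.1.2.1 drops non-serious, treatment-related Grade 1 events from the recorded data even when the protocol changes treatment because of them. Section 6.1.2.2 leaves out systemic steroids given for adverse events, although the protocol acts on their dose and duration.

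The effect is confined to recorded and reported toxicity. Patients and dose decisions remain protected, and the response endpoint is not affected. Section 10.1 is not itself in error, since it promises tables of recorded toxicity only.

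The number of affected patients may be zero. The upper expected figures at the accrual ceiling are about 3 for pneumonitis and 4 for infusion reaction. They rest on pembrolizumab-alone rates carrying over to the combination and on every Grade 1 to 2 case being Grade 1. Rash adds an amount that the documents do not allow to be estimated. Confidence is high on the text of the rules and low on the count.

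**What to change.** In 6.1.2.1, exempt from the first bullet any treatment-related Grade 1 event that leads to a dose hold, infusion-rate change, dose change, systemic steroid treatment or discontinuation, or that counts as a DLT. In 6.1.2.2, capture systemic corticosteroids given for immune-related adverse events, with drug, dose, and start and stop dates. Leave the general Grade 1 exclusion and the bullet on unrelated Grade 2 events as they are.

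The cost is one sentence in each section and a few extra entries copied from source records that already exist. On the upper assumptions, the tops of the ranges are 6 pneumonitis and 8 infusion-reaction patients in 85. Rash cases that lead to a hold and steroid courses for immune-related events come on top of that.

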7.4 NIH REQUIRED DATA AND SAFETY MONITORING PLAN

7.4.1 Principal Investigator/Research Team

The clinical research team will meet weekly when patients are being actively treated on the trial to discuss each patient in detail. Decisions about dose level enrollment and dose escalation if applicable will be made based on the toxicity data from prior patients.

All data will be collected in a timely manner and reviewed by the principal investigator or a clinical associate investigator in a timely manner. Events meeting requirements for expedited reporting as described in Section 7.2.1 will be submitted within the appropriate timelines.

The principal investigator will review adverse event and response data on each patient to ensure safety and data accuracy. The principal investigator will personally conduct or supervise the investigation and provide appropriate delegation of responsibilities to other members of the research staff.

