8.1.5 Relationship to Study Product

All AEs will have their relationship to study product assessed using the terms: related or not related.

- Related There is a reasonable possibility that the study product caused the adverse event. Reasonable possibility means that there is evidence to suggest a causal relationship between the study product and the adverse event.
- Not Related There is not a reasonable possibility that the administration of the study product caused the event.

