8.2 ASSESSMENT OF SAFETY EVENTS

AE information collected will include event description, date of onset, assessment of severity and relationship to study product and alternate etiology (if not related to study product), date of resolution of the event, seriousness and outcome. The assessment of severity and relationship to the study product will be done only by those with the training and authority to make a diagnosis and listed on the Form FDA 1572 as the site principal investigator or sub-investigator. AEs occurring during the collection and reporting period will be documented appropriately regardless of relationship. AEs will be followed through resolution.

SAEs will be:

- Assessed for severity and relationship to study product and alternate etiology (if not related to study product) by a licensed study physician listed on the Form FDA 1572 as the site principal investigator or sub-investigator.
- Recorded on the appropriate SAE report form, the medical record and captured in the clinical database.

• Followed through resolution by a licensed study physician listed on the Form FDA 1572 as the site principal investigator or sub-investigator.

For timeframe of recording adverse events, please refer to Section 6.1. All serious adverse events recorded from the time of first investigational product administration must be reported to the Sponsor with the exception of any listed in Section 8.4.

8.3 **Reporting of Serious Adverse Events**

Any AE that meets protocol-defined serious criteria or meets the definition of Adverse Event of Special Interest that require expedited reporting must be submitted immediately (within 24 hours of awareness) to OSRO Safety using the CCR SAE report form. Any exceptions to the expedited reporting requirements are found in Section **8.4**.

All SAE reporting must include the elements described in Section 8.2.

SAE reports will be submitted to the Center for Cancer Research (CCR) at: [contact] and to the CCR PI and study coordinator. CCR SAE report form and instructions can be found at: https://ccrod.cancer.gov/confluence/display/CCRCRO/Forms+and+Instructions

Following the assessment of the SAE by OSRO, other supporting documentation of the event may be requested by the OSRO Safety and should be provided as soon as possible.

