10.1 METHODS OF ANALYSIS

Response rates will be calculated as the percent of patients whose best response is a CR or PR. Toxicity information recorded will include the type, severity, time of onset, time of resolution, and the probable association with the study regimen. Tables will be constructed to summarize the observed incidence by severity and type of toxicity.

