13.3 Pembrolizumab

(Refer to FDA-approved package insert for complete product information)

13.3.1 Description:

Pembrolizumab is a humanized monoclonal IgG4 antibody directed against the human cell surface receptor, programmed death-1, (PD-1). Following administration, pembrolizumab binds to PD-1 and blocks the interaction between PD-1 and its ligands.

13.3.2 How Supplied:

Keytruda (pembrolizumab) will be purchased by the NIH Clinical Center Pharmacy Department from commercial sources. Pembrolizumab is supplied in a single-use 50 mg vial as pembrolizumab lyophilized powder and as a single use 25 mg/mL ready-to-use solution containing 4 mL (100 mg/vial).

13.3.3 Reconstitution/Dose Preparation:

The lyophilized powder is reconstituted with 2.3 mL Sterile Water for injection, USP, and the resultant concentration is 25 mg/mL. Diluent should be directed against the side of the vial to avoid excess foaming. Swirl contents gently until completely dissolved. Let contents sit for up to 5 minutes to allow all bubbles to clear. Do not shake.

The ready-to-use solution or reconstituted lyophilized powder must be further diluted prior to administration. It may be diluted in 0.9% Sodium Chloride injection, USP or 5% Dextrose Injection, USP. The final concentration of the dilution solution should be between 1 mg/ml to 10 mg/ml.

13.3.4 Stability/Storage:

The reconstituted lyophilized power is stable for up to 6 hours at room temperature or up to 24 hours at when stored under refrigeration (2-8°C or 36-46°F).

The diluted solution is stable for up to 6 hours at room temperature or up to 24 hours at when stored under refrigeration (2-8°C or 36-46°F).

13.3.5 Administration:

Pembrolizumab will be given at a fixed dose of 200 mg as an intravenous infusion over 30 minutes through an intravenous line containing a sterile, non-pyrogenic, low-protein binding 0.2 micron to 5 micron in-line or add-on filter.

13.3.6 Toxicities:

This protocol uses commercial supply of pembrolizumab; please refer to current FDA-approved package insert.

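### Section 6.1.2.1 leaves vascular-access-device thrombi out of the recorded data without a grade or relatedness limit, so some non-serious clots would be missing from the Section 10.1 toxicity tables

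*Combined protocol and SAP*

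**What the plan says.** Section 6.1.1 sets a general rule that all adverse events are captured. Section 6.1.2.1 then lists classes kept in source only. Three entries carry limits: Grade 1 events; Grade 2 events unrelated to treatment; and Grade 1 to 3 laboratory values that were drawn off schedule, are not clinically significant and are not tied to an adverse event. The fourth is "Events related to vascular access devices (occlusion, thrombi, hospitalizations for insertion or removal", with no limit on grade or relatedness to study drug.

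Section 10.1 describes the safety analysis: "Toxicity information recorded will include the type, severity, time of onset, time of resolution, and the probable association with the study regimen". It continues: "Tables will be constructed to summarize the observed incidence by severity and type of toxicity".

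Three other provisions bear on the point:
- Section 8.1.5 classes an event as related when "There is a reasonable possibility that the study product caused the adverse event".
- Section 8.2 requires serious adverse events to be "Recorded on the appropriate SAE report form, the medical record and captured in the clinical database".
- Section 3.1.2 defines the main form of dose-limiting toxicity as "Any Grade 3 or greater toxicity that cannot be attributed to a cause other than study treatment during the first two cycles".

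**The concern.** The other entries in Section 6.1.2.1 remove events that are mild, unrelated to treatment or clinically unimportant. The device entry removes events by where they arise. A device thrombus can thus be left out of the recorded data when a clot of the same grade and attribution at another site would be entered.

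Defining toxicities is part of the Phase I primary objective (Section 1.1.1), and the Section 10.1 tables are where they are summarized. Clots have some relevance to this regimen. Section 13.1.9 expects decitabine to raise platelet counts. Table 9 starts aspirin for thrombocytosis and holds DAC-THU at 1.2M/mcL or more. A toxicity summary for such a drug should count a recordable clot in the same way wherever it occurs.

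**Working it through.** No arithmetic applies: the plan attaches no figure to this rule and gives no device-use or thrombosis rate. The check is to follow a device-associated vessel thrombus through the recording rules.

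| Class of device thrombus | Without the device entry | With the device entry |
|---|---|---|
| Grade 1, non-serious | Not recorded (Grade 1 entry) | Not recorded |
| Grade 2, unrelated, non-serious | Not recorded (Grade 2 entry) | Not recorded |
| Grade 2, related, non-serious | Recorded | **Not recorded** |
| Grade 3, related or not, non-serious | Recorded | **Not recorded** |
| Serious, any grade | Database, through 8.2 | Database, through 8.2 |

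Only the third and fourth rows change. Three further questions follow.

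**Does another provision restore those two rows?** None does. Section 6.1.1 is the general rule that Section 6.1.2 narrows. Section 8.2 asks for adverse events to be documented, which source records alone can satisfy. Section 10.1 works from recorded toxicity. Section 6.1.2.2 also leaves out medications given to treat adverse events, so an anticoagulant started for the clot would generally leave no trace in the data.

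**Can a device clot be related to treatment?** Yes. Section 8.1.5 asks only for a reasonable possibility of causation by the study product, and a local device cause does not rule that out. The Grade 2 related row is therefore a possible class, although nothing shows that it will be populated. The Grade 3 row does not depend on relatedness.

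**How far does the serious-event route reach?** Section 8.1.2 covers death, life-threatening events and inpatient hospitalization. It also allows important medical events to be judged serious when they may jeopardize the patient and need intervention. Many Grade 3 thrombi could qualify. What remains at Grade 3 is a clot managed without admission, not life-threatening and not judged medically important.

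**The case against.** The strongest reply is that the entry already has a causal limit: it covers only events related to a device. A clot attributed to study drug that happens to lie near a line need not fall under it. Section 8.2 collects an alternate etiology for events classed as unrelated, so a clot put down to the device would ordinarily be called unrelated. At Grade 2 it would then be excluded anyway. Leaving mechanical line problems out of the database is a reasonable way to limit noise, and a clot with a local cause says little about the regimen.

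Most of this stands, and it keeps the point small. It does not remove the point. A device cause and a possible drug contribution can coexist under Section 8.1.5, and Grade 3 events elsewhere are recorded whatever their cause.

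Exposure may also be low. DAC-THU is oral. Pembrolizumab is given every three weeks "as an intravenous infusion over 30 minutes through an intravenous line". Section 11.4.1.7 adds only a possible catheter for contrast or anesthetic. No indwelling device is required.

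A reader might infer that rising platelets make thrombosis a likely toxicity here. The documents do not support that. Section 13.1.9 says a link between platelet count and thrombosis has not been evident clinically, and it expects rises especially in hyposplenic or asplenic patients. Its supporting example is a sickle cell study, so the reassurance may not carry over fully to thoracic cancer, but nothing in the documents points the other way.

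**Conclusion.** The gap is real but minor. Followed as written, Section 6.1.2.1 would keep two narrow classes out of the Section 10.1 tables: non-serious vessel thrombi at a device that are Grade 3, and those that are Grade 2 and judged possibly related to treatment. The number affected cannot be estimated from the documents; it is likely small and possibly zero. The conclusion assumes that the list is applied literally and that some patients have a device.

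Three stronger readings are not supported:
- **Serious clots are lost.** Section 8.2 sends serious adverse events to the clinical database, and the waiver in Section 8.4 covers only death or hospitalization from disease progression. Section 6.1.2.1 does not say that it yields to these sections, but that is the sensible reading.
- **Dose finding is compromised.** A clot judged to be caused by the device is ordinarily not dose-limiting under Section 3.1.2. The events remain in source, the team discusses each patient weekly, and under Section 7.4.1 "The principal investigator will review adverse event and response data on each patient to ensure safety and data accuracy".
- **Sample size shows how large the loss is.** The share that one event would make up of a cohort is only the reciprocal of the cohort size. It does not indicate how many such events will occur.

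**What to change.** Reword the fourth entry of Section 6.1.2.1 to: *Vascular access device malfunction or occlusion confined to the device lumen, and planned hospitalizations for device insertion or removal.*

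Then add: *Thrombosis of the vessel at a device is recorded under the same grade and relatedness rules as other adverse events; these exclusions do not apply to SAEs (8.2-8.3).*

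Drawing the line at the device lumen makes clear that a clot blocking only the catheter stays excluded. Limiting the admissions to planned ones matches Section 8.1.2, which exempts pre-planned stays but would not automatically exempt an unplanned removal.

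The cost is one reworded entry and one added sentence. The events are already in source. The downside is a few extra database entries, some of them for clots with a purely local device cause.
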